## **VIII. Study Procedures**

1. Parents or legal guardian(s) of patients presenting for Psychiatric Evaluation will be identified by a member of the study team
2. Research team member will screen family for firearm ownership
3. Those parents or legal guardian(s) that screen positive for having a firearm will be screened for study eligibility.
4. For those deemed eligible and consent to participate, randomization into 1 of 2 arms will occur via block randomization
5. Participants will complete pre-intervention survey
6. All participants, regardless of randomization group will receive informational resources. Informational resources will be centered around the Ohio AAP "Store It Safe" program, which focuses on harm reduction through safe storage of firearms and ammunition. This information will be provided verbally by CRC or [name] as well as in paper form.
7. Families will also receive gift card for agreeing to participate in study
8. Children/Patients may be present in the room during the gun safety intervention due to the nature of presentation to the ED. Parent/legal guardians are the primary intended audience of the intervention. Children are not a target of the intervention.
9. Patients and families randomized to receive firearm cable locks will obtain devices prior to leaving the ED
10. Follow-up surveys will be distributed via text, email or phone at approximately 4 weeks from encounter. Upon completion of the follow-up survey, a gift card will be sent via text or email provided. This information will be collected solely for the purpose of sending incentives and that information will not be used or retained in the research dataset.
11. Data collection will occur in REDCap

**Studies Using Surveys or Questionnaires:** This survey is modeled after a survey published in Pediatrics by [name]. After IRB approval, the survey will be piloted for readability and understanding among 5-10 families as well as PIRC social workers. This survey has not yet been validated. During the study CRC will be present during survey and available to read to guardian if guardian is unable to read themselves and to answer any questions the participants may have.

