#### **IV. Study Design**

This will be a prospective, non-blinded, randomized controlled study in a Pediatric Emergency Department to determine the effect of gun lock distribution with informational resources on firearm storage practices compared to informational resources alone. The study cohort includes parents or legal guardian(s) of patients presenting to the Cincinnati Children’s Hospital Emergency Department for psychiatric evaluations who have any guns in their home. Parent or guardian of the patient must be present for enrollment. Informed consent will be obtained for those families agreeing to participate in the study. Parent/guardian will be asked if they are willing to complete a survey at time of encounter and again in 4 weeks from initial encounter. If they are unable to read, the survey will be read to them by the CRC. Families will be randomized, via block randomization, into one of two study arms: (1) a control arm receiving targeted firearm safety informational resources or (2) an intervention arm, receiving targeted firearm safety informational resources in addition to the provision of 2 cable-style firearm locks. Lethal means counseling (which includes discussion about locking hazardous items such as medications and firearms) is part of the standard safety planning that occurs when PIRC counsels families. All patients will still receive standard of care counseling by PIRC team members. The informational resources provided will include more specific information and advice related to firearm safety, discussing topics such as the four pillars of safe storage and the decreased risk of suicide when firearms are stored safely. Primary outcome is change in self-reported securement of **all** firearms with a locking device. Initial survey to be given before targeted information is provided. Follow up surveys at 4-6 weeks after the ED visit will determine self-reported storage practices of firearms and medications after receiving the intervention, and Likert-scale based satisfaction with pediatric ED encounter. Follow-up attempts will be attempted via text or phone. The surveys will be available in English only. The surveys will contain only the minimum PHI needed to allow for follow-up. Survey will be electronic with responses recorded via REDCap.

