## **IX. Data Analysis/Methods**

Data will be collected in REDCap and stored on a password protected computer available only to PI and co-investigators. Frequency of responses will be calculated at the completion of data collection. Analysis will be performed by the study team at CCHMC. Primary outcome is change in self-reported securement of **all** firearms with a locking device. This will be elucidated by comparing responses to the pre and post intervention surveys. Frequencies will be compared between the two study arms. For our secondary outcomes, questions regarding degree of satisfaction (which will be assessed via Likert scale), removal/acquisition of firearms, and (if applicable) use of provided gun locks. Based on prior studies that compared counseling to receipt of tangible resource, we can expect a 25% difference between

the groups. We will need 138 participants to detect a difference of this magnitude. Assuming a dropout rate of 30% a sample size of 200 will be necessary. The most recent CCHMC PIRC data show that 40-100 patient-families each month have reported gun ownership (This number is 100-150 pre-COVID). A Chi Squared test will be used to determine significance difference of proportions between the two groups. Limitations of our study include self-reporting of ownership and storage. This may be further limited as families who do not store weapon safely may be less likely to report ownership.

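### Randomisation is listed before the self-reported baseline survey in an unblinded trial, and nothing withholds the arm until that survey is complete

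*Combined protocol and SAP*

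**What the plan says.** Section VIII (Study Procedures) gives a numbered list.

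- Step 4: "For those deemed eligible and consent to participate, randomization into 1 of 2 arms will occur via block randomization".
- Step 5: "Participants will complete pre-intervention survey".
- Step 6: both arms receive the same firearm-safety information. "This information will be provided verbally by CRC or [name] as well as in paper form".
- Step 9: "Patients and families randomized to receive firearm cable locks will obtain devices prior to leaving the ED".

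The survey paragraph under the list adds: "During the study CRC will be present during survey and available to read to guardian". The CRC also answers participants' questions.

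Section IV (Study Design) states: "This will be a prospective, non-blinded, randomized controlled study". Its one rule on the timing of the baseline survey is: "Initial survey to be given before targeted information is provided".

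Section IX (Data Analysis/Methods) names change in self-reported securement of all firearms as the primary outcome and says of it: "This will be elucidated by comparing responses to the pre and post intervention surveys". The test is a chi-squared comparison of proportions between arms.

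**The concern.** The baseline survey is a self-report and one of the two measurements behind the primary outcome. Its value as a baseline depends on its being unaffected by the allocation. The listed order puts allocation first, in a trial without blinding, with a CRC in the room.

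Two routes to bias are open if the arm is known early. A family that expects locks may describe its current storage differently from one that does not. The CRC, who may deliver the information meant to be identical in both arms, may also give it with different emphasis. The first distorts the measured change. The second makes the arms differ by more than the locks.

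Lack of blinding after lock handover cannot be avoided in this design. Knowledge of the arm before baseline can be.

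**Working it through.** **1. Order of events.** Steps 4, 5, 6 and 9 run: allocate, measure baseline, inform, hand over locks. The Section IV rule orders the survey against the information. It does not order the survey against allocation or against disclosure of the arm. No section describes allocation concealment. Step 6 is the same in both arms, so the arm is first needed at step 9.

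**2. The plan's own figures.** Section IX gives 138 evaluable participants and 30% dropout: 138 / 0.70 = 197.1, rounded up to 198, which agrees with the stated 200. Reordering the steps changes neither 138 nor 200. With equal allocation (assumed; the ratio is not stated), 138 / 2 = 69 per arm.

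**3. How far arm-aware baseline answers could matter.** Everything here except the 138 is an assumption: 69 per arm, 40% of families truly all-secured at baseline, 30% of the unsecured converting by follow-up, 95% of the secured staying so, no treatment effect, two-sided 5% test, and misreporting at baseline in one arm only.

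- Newly secured, no misreporting: 0.60 × 0.30 = 18.0%.
- Baseline reported *d* too low (secured families reporting unsecured): 18.0% + *d* × 0.95. For *d* = 5 points, 22.75%; for 10 points, 27.5%.
- Baseline reported *d* too high (unsecured families reporting secured): 18.0% − *d* × 0.30. For 5 points, 16.5%; for 10 points, 15.0%.
- Follow-up status: 0.40 × 0.95 + 0.60 × 0.30 = 56% in both arms, whatever was said at baseline.

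The newly-secured row and the follow-up result (4.8%) come from exact enumeration of the Pearson chi-squared test. The mean-change and adjusted rows come from simulation with 40,000 replicates. False-positive rates:

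| Analysis | 5 low | 10 low | 5 high | 10 high |
|---|---|---|---|---|
| Newly secured, chi-squared (5.0% without misreporting) | 10.7% | 26.7% | 5.6% | 7.5% |
| Mean pre-to-post change, t-type test | 10.4% | 25.9% | 10.0% | 25.0% |
| Follow-up adjusted for reported baseline, linear model | 7.5% | 14.0% | 7.3% | 12.5% |
| Follow-up status alone, chi-squared | 4.8% | 4.8% | 4.8% | 4.8% |

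**4. Sensitivity.** Over the 27 combinations of baseline 20, 40 or 60%, conversion 20, 30 or 50%, and staying secured 90, 95 or 100%, the newly-secured rates run as follows:

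- 5 points low: 8.0–15.8%
- 10 points low: 18.3–41.7%
- 5 points high: 5.2–6.6%
- 10 points high: 6.1–12.0%

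Differential emphasis in the verbal information is not modelled.

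**The case against.** The strongest reply is that the text is silent and does not state a fault. Randomising at step 4 is not the same as announcing the arm at step 4, and the list is not strictly chronological: steps 8 and 11 are general remarks. The baseline is also partly protected, because the survey must precede the targeted information, the most obvious influence on the answers. The proposed mechanism has no known direction, and the inflated error rates follow from misreporting that was assumed. Much of the exposure comes from an unsettled endpoint: the Section II hypothesis can be read as a comparison of follow-up status alone, and on that reading the baseline bias disappears. Follow-up remains unblinded self-report whatever the order.

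All of this is fair as a limit on what can be claimed. Early disclosure is not shown, and the figures do not show that misreporting occurs. It does not close the gap. Steps 4 to 6 read as a sequence, no other text puts the survey ahead of allocation, and the Section IV rule does not cover knowledge of the arm. Section IX specifies a pre/post comparison, and nothing commits the trial to follow-up status only. The remaining follow-up problem, of which Section IX lists only the self-report part as a limitation, is no reason to leave an avoidable one at baseline.

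**Conclusion.** The concern holds, as a missing safeguard and not as demonstrated bias. The listed order exposes a self-reported component of the primary outcome to knowledge of the arm, and nothing in the design requires that order. The possible effect ranges from none (follow-up status alone) to a false-positive rate of about a quarter (10 points of one-arm under-reporting at baseline, analysed as newly secured, or 10 points in either direction analysed as mean change), under the central assumptions. Over-reporting does little if the outcome is newly secured. These sizes rest on assumed storage rates, assumed misreporting and equal allocation; the documents give no estimate of any of them. It should be fixed, because the exposure touches the primary outcome and is cheap to remove.

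**What to change.** Reorder Section VIII as follows:

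1. Consent.
2. Baseline survey completed and locked in REDCap.
3. Common verbal and paper information given.
4. Randomisation, or opening of the allocation.
5. Lock handover in the intervention arm.

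This order protects both the baseline answers and the common information.

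At a minimum, add one sentence stating that the arm is concealed from the family and the CRC until the baseline survey is locked. That protects the baseline only; it does not prevent different emphasis in the information that follows.

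For any family already enrolled with the arm known before the survey, report follow-up status by arm as a sensitivity analysis, since it does not use the baseline answers. It would not correct for differences in how the information was given, nor for unblinded self-report at follow-up.

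The cost is a short protocol amendment. REDCap is already the data system, the sample size is unchanged, and no staff, visits or data items are added.

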## **IX. Data Analysis/Methods**

Data will be collected in REDCap and stored on a password protected computer available only to PI and co-investigators. Frequency of responses will be calculated at the completion of data collection. Analysis will be performed by the study team at CCHMC. Primary outcome is change in self-reported securement of **all** firearms with a locking device. This will be elucidated by comparing responses to the pre and post intervention surveys. Frequencies will be compared between the two study arms. For our secondary outcomes, questions regarding degree of satisfaction (which will be assessed via Likert scale), removal/acquisition of firearms, and (if applicable) use of provided gun locks. Based on prior studies that compared counseling to receipt of tangible resource, we can expect a 25% difference between

the groups. We will need 138 participants to detect a difference of this magnitude. Assuming a dropout rate of 30% a sample size of 200 will be necessary. The most recent CCHMC PIRC data show that 40-100 patient-families each month have reported gun ownership (This number is 100-150 pre-COVID). A Chi Squared test will be used to determine significance difference of proportions between the two groups. Limitations of our study include self-reporting of ownership and storage. This may be further limited as families who do not store weapon safely may be less likely to report ownership.

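### With 30% of families expected to be lost, the plan's only test defaults to respondents; that comparison can be biased if the link between storage and response differs by arm, and baseline storage is not used to correct it

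*Combined protocol and SAP*

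**What the plan says.** Section IX takes the primary outcome, change in self-reported securement of all firearms, from two surveys: "This will be elucidated by comparing responses to the pre and post intervention surveys". A family that does not return the second survey therefore has no outcome.

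On size, the section says "We will need 138 participants to detect a difference of this magnitude" and then "Assuming a dropout rate of 30% a sample size of 200 will be necessary". On analysis it says "A Chi Squared test will be used to determine significance difference of proportions between the two groups".

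Section IV describes a "prospective, non-blinded, randomized controlled study". Section VIII has participants complete a pre-intervention survey, so baseline storage is planned for every participant.

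No section defines an analysis population, a missing-data method, a comparison of responders with non-responders, or a sensitivity analysis. The limitations listed in Section IX cover self-report and under-reporting of ownership, not loss to follow-up.

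**The concern.** Enrolling 200 to keep about 138 protects power if non-response is unrelated to storage. It does nothing about who the respondents are.

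Families know their arm, and follow-up is remote. Section IX also plans to ask about use of the provided locks. A lock-arm family that left the locks unused has a reason not to reply that a control family does not have. Section IX already accepts a similar mechanism at enrolment, where it says that families with unsafe storage may be less likely to report ownership.

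If that selection differs by arm, the respondents no longer compare like with like. An effect could then be created or hidden. Similar overall response rates would not rule this out, because the mix of families behind each rate can still differ.

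**Working it through.** **Inputs from the documents.** 138 evaluable, 30% dropout, 200 randomised, chi-square test (Section IX); two arms by block randomisation (Section IV).

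**Assumptions, because the documents are silent.** 1:1 allocation; two-sided 5% level. Storage model: 40% of families all-secured at baseline, 95% of those still secured at follow-up, 30% of the others newly secured, no arm effect. Control response is 70% whatever the storage. Lock-arm response is 85% if secured at baseline and 60% if not.

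**1. The plan's own figure.** 138 / (1 − 0.30) = 197.1, or 198 for two equal arms; the plan states 200. Then 200 × 0.70 = 140 respondents, about 70 per arm. The inflation is arithmetically sound.

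**2. Respondents only, post-survey status.**
- True rate in each arm: 0.40 × 0.95 + 0.60 × 0.30 = 0.56.
- Lock-arm response: 0.40 × 0.85 + 0.60 × 0.60 = 0.34 + 0.36 = 0.70, the same as control.
- Share of lock-arm respondents secured at baseline: 0.34 / 0.70 = 0.486.
- Observed lock-arm rate: 0.486 × 0.95 + 0.514 × 0.30 = 0.616. Control stays at 0.56.
- Bias: +5.6 points. In 20,000 simulated trials of 100 per arm the chi-square rejected in 10.4%; repeat simulations gave 10% to 11%.

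**3. The same data standardised to the baseline storage of all 200.** The lock arm becomes 0.40 × 0.95 + 0.60 × 0.30 = 0.56, so the bias is 0. Simulated false positives were 5.5% (5% to 6% across repeats). With harmless loss and a true 25-point effect, standardising raised power from about 90% to 96%.

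**4. Same response pattern in both arms.** With 85%/60% in both arms the bias is 0 and rejection about 5%. False positives need a pattern that differs by arm.

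**5. Other codings of change, with the inputs of step 2.**
- Newly secured, among all respondents: 0.514 × 0.30 − 0.60 × 0.30 = −2.6 points, with 6.8% rejection.
- Conversion among those unsecured at baseline: 0.30 in both arms, so essentially no bias and 5.0% rejection.

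**6. Lock-arm response depends on the unseen follow-up status (85% if secured, 55% if not).**
- Unadjusted: 0.56 × 0.85 / (0.56 × 0.85 + 0.44 × 0.55) = 0.476 / 0.718 = 0.663, a bias of +10.3 points.
- Secured at baseline: 0.8075 / (0.8075 + 0.0275) = 0.967.
- Not secured at baseline: 0.255 / (0.255 + 0.385) = 0.398.
- Standardised: 0.40 × 0.967 + 0.60 × 0.398 = 0.626. About +6.6 points remain, with about 17% false positives.
- At 80%/60%, +4.3 points and 11% remain after standardising.

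**7. Hiding an effect.** Take true rates of 37.5% and 62.5%. Power with 70 per arm is 85% if loss is unrelated to storage. Suppose control response is 80% if locked and 60% if not. The control rate then appears as 0.300 / 0.675 = 0.444, the difference falls to 18.1 points and power to 57%.

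**8. Carrying baseline status forward for non-responders.** With harmless 30% loss a true 25-point effect shrinks to 0.70 × 25 = 17.5 points. Requiring significance under that rule would cut power from about 90% to a little over 70%.

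**The case against.** **No bias has been shown.** Every response rate above by arm or storage status is assumed. A reader might infer that the stated test, followed exactly, must give a biased answer. The documents do not support that, because they give no response data by arm or storage status.

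**Storage-related non-response is not enough.** A reader might also infer that any link between storage and response invalidates the chi-square. Step 4 shows otherwise for a test of no effect.

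**The respondents-only analysis is an inference.** Section IX names no analysis set, and a chi-square on all 200 is possible if missing families are counted as not locked. That is true, but it needs a rule that the plan does not contain. Without one, the outcome definition leads to respondents only.

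**The figures depend on coding.** Section IX speaks of change, while step 2 uses post-survey status. Step 5 shows that the bias can shrink or reverse. The size is therefore illustrative.

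**Existing safeguards.** There is a gift card for completing follow-up (Sections VIII and XVII), contact by text, email or phone (Section VIII), and exclusion of guardians unwilling or unable to answer follow-up (Section VI). These may make a large one-arm gap less likely. They do not address selection among the 30% still expected to be lost.

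**Baseline adjustment is not a full cure.** Step 6 confirms this. It is why sensitivity analyses are needed as well.

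**Conclusion.** The concern holds as a conditional risk. The plan expects 30% loss, defaults to a comparison of respondents, and leaves unused the baseline information that could correct part of the problem. Under the stated assumptions the bias is about +5.6 points with about 10% false positives, and standardising to baseline storage removes it. If response depends on unseen follow-up storage, adjustment removes only part: +10.3 points falls to +6.6 at 85%/55%.

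These sizes rest on assumed response rates, an assumed storage model, 1:1 allocation, a two-sided 5% level and post-survey status as the outcome.

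A reader might also note that 30% missing in each arm leaves worst-case bounds 60 points wide against a 25-point target. That holds for any binary outcome with this much loss and says nothing specific about this plan, so it carries no weight here.

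The change should be made before follow-up outcomes are seen. Confidence is medium.

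**What to change.** In Section IX:

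- Make the primary comparison all randomised families by assigned arm. Use baseline all-secured status from the pre-intervention survey, through standardisation or multiple imputation within arm.
- State how change is coded, since the direction of any bias depends on it.
- Report response rates by arm and by baseline storage status.
- Add two sensitivity analyses: (1) non-responders keep their baseline status; (2) a tipping-point table that lowers the assumed secured rate among lock-arm non-responders until significance is lost. Both should be supportive and not a condition for claiming an effect, given the loss of power in step 8.
- State that the exclusion for guardians unwilling or unable to answer follow-up applies only before randomisation. Applied later, it would remove non-responders.

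Section VIII places the baseline survey after randomisation, so the plan should also confirm that it is completed before the family learns its arm.

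The cost is plan wording and a few hours of programming, with no extra families, visits or data. The result may look less favourable under the sensitivity analyses.

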#### **II. Purpose of Study**

The primary purpose of this study is to determine if distribution of informational resources (such as handouts) coupled with distribution of firearm safety locks, improves self-reported securement of all firearms with locking devices (ie. cable lock, lockbox, gun safe) over informational resources alone. Secondary objectives include: reporting how families view ED-based firearm safety counseling and describing relative improvement among other lethal means safety measures: (1) firearms stored unloaded (2) firearms acquired/removed from the home, (3) medications stored with locking device and (4) medications removed from the home. Our study will focus on families of children presenting for psychiatric evaluation in a pediatric emergency department. We hypothesize that families that receive informational resources and firearm locks will report all firearms stored with a locking device 25% more frequently than families who receive informational resources alone.

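### The primary chi-square does not condition on baseline all-firearm securement, so a valid test loses power and is exposed to chance baseline imbalance

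*Combined protocol and SAP*

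**What the plan says.** Section IX (Data Analysis/Methods) names change in self-reported securement of every firearm as the primary outcome and explains: "This will be elucidated by comparing responses to the pre and post intervention surveys". The only test is: "A Chi Squared test will be used to determine significance difference of proportions between the two groups". No covariate or stratum is given. Sections IV and VIII describe block randomisation without a stratification factor.

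Section II states the hypothesis as follow-up status: families given locks "will report all firearms stored with a locking device 25% more frequently than families who receive informational resources alone".

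Baseline storage is recorded. Section IV places the initial survey before the information is given, and Section VIII lists it as step 5, after randomisation at step 4. Section VI screens on firearm possession and sets no condition on current storage.

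On size, Section IX says "We will need 138 participants to detect a difference of this magnitude" and "Assuming a dropout rate of 30% a sample size of 200 will be necessary".

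**The concern.** A family that already locks every firearm cannot improve, and its follow-up answer is probably well predicted by its baseline answer. An analysis that leaves baseline out gives up that information and lets a chance difference in the share already secured feed into the treatment comparison.

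The plan gives no rule for coding change for each family. Three natural readings are:

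1. **Follow-up status** (secured or not), as in the Section II hypothesis. Baseline is ignored.
2. **Improved** (unsecured to secured) among all families. Families who stay secured count as failures, and a secured family that becomes unsecured is not registered. That can happen, since Section II itself lists "firearms acquired/removed from the home" among its secondary measures.
3. **Conversion among baseline-unsecured families only.** This does condition on baseline, but answers a narrower question.

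Other codings are possible, such as improved/unchanged/worsened, and an unstratified test of those would not adjust for baseline either. The plan does not choose reading 3, and its sample size allows only for dropout, not for setting aside families already secured. The point therefore concerns readings 1 and 2. What is at stake is efficiency and robustness in a single trial of about 138 evaluable families, not the validity of the test.

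**Working it through.** **Inputs from the plan (Section IX).** 138 evaluable families, 30% dropout, 200 enrolled, a 25% difference. I take this as 25 percentage points with 1:1 allocation, so 69 per arm; both are assumptions.

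**Inputs not in the plan.** Alpha, power, control rate, baseline all-locked rate and transition rates. The nearest figure is in Section III: under 40% of gun-owning families meet the stricter AAP storage definition. Base-case assumptions: 40% secured at baseline, 95% of those stay secured in both arms, 30% of unsecured control families convert. Tests are two-sided at 5%.

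**Step 1. The plan's own figure.** It cannot be reproduced uniquely, but it is attainable. With control 32% v 57% and 80% power, n per arm = [1.96·√(2×0.445×0.555) + 0.842·√(0.32×0.68 + 0.57×0.43)]² / 0.25² ≈ 60.8. The continuity correction raises this to 69, or 138 in total. The same total arises for control rates of about 30.5–33.5% or 41.5–44.5%. Without the correction, 80% power never needs more than 124. For dropout, 138/0.7 = 197, stated as 200. Nothing is left for excluding families already secured.

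**Step 2. Size of chance imbalance.** SD of the between-arm baseline difference = √(2×0.4×0.6/69) = 0.083, or 8.3 points.

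**Step 3. Effect on the estimate.** For an overall difference of 25 points, intervention conversion must be 0.30 + 0.25/0.60 = 0.717.
- Follow-up status: slope = [(0.95−0.30) + (0.95−0.717)]/2 = +0.44, so one SD moves the estimate by 0.44×8.3 = +3.7 points.
- Improved among all: slope = −(0.30+0.717)/2 = −0.51, so one SD moves it by −4.2 points.
- Stratified by baseline: slope 0.

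With 80% staying secured, the follow-up slope is [(0.80−0.30) + (0.80−0.717)]/2 = 0.29, or +2.4 points.

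**Step 4. Power, base case (300,000 simulated trials per effect).**

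| Analysis | 25 points | 20 points | 15 points |
|---|---|---|---|
| Follow-up status, chi-square | 89.8% | 70.5% | 44.4% |
| Follow-up status, stratified by baseline | 95.4% | 82.4% | 58.4% |
| Improved among all, chi-square | 90.4% | 75.6% | 53.2% |
| Conversion among unsecured, chi-square | 97.5% | 87.2% | 64.2% |

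Type I error was 4.7–5.3% for every test over 54 null scenarios.

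**Step 5. Power given an imbalance.** An imbalance of at least 1 SD occurs in about 17% of trials in each direction. At 25 points, when the intervention arm has more or fewer secured families, power is 99% or 73% for follow-up status, 71% or 99% for improved, and 95% either way when stratified. With 80% staying secured it is 94% or 75% for follow-up status, against 89% either way when stratified. With no true effect, and the lock arm at least 10 points ahead at baseline, the unadjusted follow-up test rejects in 13–16% of trials and the stratified test in 4–5% (30–50% secured, 90–95% staying secured, 20% conversion).

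**Step 6. Varying the assumptions.** The grid has 156 non-null scenarios: 20/40/60% secured, 70–95% staying secured, control conversion 20/30/40%, differences of 15/20/25 points.
- Stratified v unadjusted follow-up: ahead in 152, range −0.9 to +20.4 points. The median gain falls from 8.4 points at 95% staying secured to 1.9 at 70%. The four exceptions all have 60% secured and 70–75% staying secured.
- Conversion among unsecured v improved among all: ahead in all 156, by 2.3 to 27.1 points.
- Improved among all v stratified follow-up: improved is level or ahead in 85 of 156, and by 10 points or more in 17, all with 85% or fewer staying secured. Example: 61.6% v 51.0% (60% secured, 80% staying secured, 30% control conversion, 15 points).

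The grid puts the whole effect among unsecured families. If locks also help families stay secured (90% v 80%, 20 points in total, 40% secured), power is 66.8% for follow-up status, 58.1% for improved, 75.9% for stratified follow-up and 69.6% for conversion.

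**The case against.** **The test is not wrong.** An unadjusted chi-square is standard in a randomised trial and holds its error rate. At the planned 25 points with 40% secured, it has roughly 85–90% power across the range examined. This stands, and it is why the point is not one of validity.

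**The base case is favourable.** Having 95% stay secured is the top of the range examined, and the plan's own cautions point to a noisier measure: "This survey has not yet been validated" (Section VIII) and "Limitations of our study include self-reporting of ownership and storage" (Section IX). This also stands. At 40% secured and 30% control conversion, the gains from stratifying at 25/20/15 points are about 6/12/14 with 95% staying secured, 3.1/5.9/6.2 with 80%, and 1.5/2.7/2.8 with 70%.

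**Part of the trouble is the undefined endpoint.** In the base case, readings 1 and 2 give different significance verdicts on the same data in 14%, 29% and 36% of trials at 25, 20 and 15 points. Conditioning alone does not cure that: stratified follow-up and conversion among unsecured families still disagree in 2.9%, 7.6% and 11.6%. Only naming the endpoint does, so the fix must do both.

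**Coverage of all families is inferred.** It is. The wording compares the two arms without restriction, but under reading 3 the criticism would not apply.

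**Baseline is listed after randomisation in a non-blinded trial.** If answers reflected knowledge of the arm, stratifying on them could introduce bias. Nothing says families learn their arm first, but the order should be secured.

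**Conclusion.** The concern holds as a matter of efficiency and robustness. If the chi-square is run on all families, by follow-up status or by improvement, it leaves out a baseline measure that is already collected and probably prognostic. In the base case, stratifying adds about 6 to 14 points of power to the follow-up comparison and removes a shift of 3.7 points per SD of chance imbalance. With 70% staying secured the gain is only 1.5 to 2.8 points, and it is about zero or slightly negative in the few scenarios with 60% secured and 70–75% staying secured.

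The sizes rest wholly on assumed baseline and transition rates, 1:1 allocation, a two-sided 5% level and baseline answers unaffected by arm. The direction of the imbalance effect does not depend on the base case: over all non-null scenarios the slope is +0.05 to +0.65 for follow-up status and −0.29 to −0.65 for improved, and within 0.013 of zero when stratified. The change should be made, with medium confidence in its size.

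**What to change.** Replace the test sentence in Section IX with text such as:

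> The primary endpoint is every firearm reported as locked at follow-up (yes/no). Arms will be compared by a Mantel-Haenszel risk difference with 95% confidence interval, stratified by whether every firearm was locked at baseline.

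Logistic regression on arm and baseline, with a standardised risk difference, is an acceptable alternative. Keep the unadjusted chi-square on follow-up status as a sensitivity analysis. Report conversion among baseline-unsecured families, and the number moving from secured to unsecured, as supporting analyses. In simulation the Mantel-Haenszel interval covered 94.6–96.6%, with type I error 5.2–5.4%.

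If improvement is preferred as the primary endpoint, define it as conversion among baseline-unsecured families and recheck the 138. At 40% secured, only about 0.6×69 = 41 per arm contribute; if the planned 25 points is the difference within that group (30% v 55%), power is 64%.

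In Section VIII, have the baseline survey completed before allocation is revealed.

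**Cost.** A few lines of text and one stratified estimate, with no extra families or data items. The trade-off is that improved among all families can have more power than stratified follow-up when fewer families stay secured, but it stays exposed to imbalance and cannot register families that become unsecured.
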